5.6 Variable conversion

No variable conversion is performed.

6 Statistical processing

6.1 Confidence interval/significance level

The significance level of hypothesis testing will be two-sided 5%. A two-sided 95% confidence interval will be calculated if interval estimation is performed.

6.2 Multiple comparisons/multiplicity

Multiplicity will not be adjusted.

6.3 Details of statistical analysis

6.3.1 Summary statistics

If summary statistics is described in this plan, the following values will be calculated unless otherwise specified.

Number of subjects, number of subjects with missing, mean, standard deviation, minimum value, quartile point (25% point, 50% point [median], 75% point), maximum value

6.3.2 Number of digits

Percentages will be rounded to 1 decimal place for the fraction distribution, unless the details of the individual items are specified. Among the summary statistics (number of subjects, mean standard deviation, minimum value, quartiles (25% point, 50% point [median], 75% point), and maximum value), the mean, standard deviation, and quartiles (25% point, 50% point [median], 75% point) are rounded up to where a decimal place is one digit below the original data.

7 Analysis of primary endpoints

7.1 Patient characteristics at baseline (at the start of the first-line chemotherapy and at the start of the avelumab administration)

Target : Analysis set

populatio

n

Endpoints : 1) Primary lesion at initial diagnosis

Categorical Variable

Site of the primary tumor
Histology of primary lesion¹⁾
Presence or absence of variant histology
 Subtype
Histologic dysplasia
 Two-step grade
 Three-step grade
Histological depth
Presence/absence of definitive treatment of primary lesion
 Treatment
 Surgery

2) At the start of the first-line chemotherapy

Continuous variable

Number of cycles of first-line chemotherapy
Number of cycles at the evaluation of best overall response to first-line chemotherapies
Treatment-free interval: Time from the end of first-line chemotherapy to the start date of avelumab administration (days)
Duration of first-line chemotherapy (days)

Categorical Variable

ECOG Performance Status
Karnofsky performance status (%)
Karnofsky performance status (2 divisions)
Bajorin risk classification
Staging (TNM classification)
 Primary tumor (T factor)
 Metastases to regional lymph nodes (N factor)
 Distant metastasis (M factor)
Clinical Stage
 Bladder
 Urethra
 Renal pelvis and ureter
Presence/absence of distant metastasis

distant metastasis site
Presence or absence of visceral metastasis
Presence or absence of non-visceral metastasis
Number of metastatic organs
Number of metastases in one organ
Number of distant metastases
Presence/absence of local recurrence
Regimen for first-line chemotherapy
Best overall response to first-line chemotherapies

3) At the start of avelumab administration

Continuous variable

Age

Categorical Variable

Gender
ECOG Performance Status
Karnofsky performance status (%)
Karnofsky performance status (2 divisions)
Bajorin risk classification
Staging (TNM classification)
 Primary tumor (T factor)
 Metastases to regional lymph nodes (N factor)
 Distant metastasis (M factor)
Clinical Stage
 Bladder
 Urethra
 Renal pelvis and ureter
Presence/absence of distant metastasis
 Site of distant metastasis
 Presence or absence of visceral metastasis
 Presence or absence of non-visceral metastasis
 Presence or absence of past medical history²⁾
 Details of past medical history
 Details of past medical history of auto-immune disease
 Details of other medical history

Presence or absence of complication²⁾

 Details of Complication

 Details of complication of auto-immune disease

 Details of other complications

Presence/absence of concomitant medication with steroid or immunosuppressant

 Details of concomitant drugs using steroids and immunosuppressants

1) If multiple selections are made, the following will be used to determine the tissue type:

Small cell carcinoma > Urothelial carcinoma > It is determined by the order of predominant histological type in terms of quantity.

- i. If there is any "small cell carcinoma," "small cell carcinoma" is adopted. (If both small cell carcinoma and urothelial carcinoma are selected, small cell carcinoma is adopted.)
- ii. If there is no "small cell carcinoma," and "urothelial carcinoma" exists, "urothelial carcinoma" is adopted.
- iii. If neither "small cell carcinoma" nor "urothelial carcinoma" exists, the tissue type listed in the EDC comment section as the predominant tissue type in terms of quantity is adopted.

2) If disease is cured by the start of avelumab administration, it is regarded as past medical history. If it is continued after the administration of avelumab, it is regarded as complication.

Statistical analysis : The following tabulation will be performed for end points.

Summary statistics will be calculated for continuous variables.

A frequency table (number of subjects, proportion (%)) will be prepared for categorical variables.

A frequency table (number of subjects and proportion (%)) will be prepared also for the details of past medical history of auto-immune disease, other past medical history, complication of auto-immune disease, other complication, and concomitant medications of steroids and immunosuppressants.

【Division of categorical variables】

Factor	Division
--------	----------

Site of the primary tumor	bladder/urethra/renal pelvis/ureter
Histology of primary lesion	Urothelial carcinoma/adenocarcinoma/squamous cell carcinoma/small cell carcinoma/other
Presence or absence of variant histology	presence/absence/unknown
Subtype	nested, including large nested/microcystic/micropapillary/lymphoepithelioma-like/plasmacytoid/signet ring cell/diffuse/sarcomatoid/giant cell/poorly differentiated/lipid-rich/clear cell/other
Histologic dysplasia	two step grades (low grade, high grade)/three step grades (G1, G2, G3)/unknown
Histologic dysplasia: two-step grade	low grade/high grade
Histologic dysplasia: three-step grade	G1/G2/G3
Histological depth	Bladder: pTX/pT0/pTa/pTis/pT1/pT2a/pT2b/pT3a/pT3bpT4a/pT4b Urethra: pTX/pT0/pTa/pTis/pT1/pT2/pT3/pT4 Renal pelvis: pTX/pT0/pTa/pTis/pT1/pT2/pT3/pT4 Ureter: pTX/pT0/pTa/pTis/pT1/pT2/pT3/pT4
Presence/absence of definitive treatment of primary lesion	absence/presence/unknown
Treatment	surgery/others
Surgery	Data will be aggregated based on the combination of the data obtained.
Gender	male/female
ECOG Performance Status	0/1/2/3/4
Karnofsky performance status (%)	100/90/80/70/60/50/40/30/20/10/0
Karnofsky performance status (2 divisions)	<80%/>=80%
Bajorin risk classification	0 (no risk factor)/1 (single risk factor)/2 (two risk factors)
Staging (TNM classification): Primary tumor (T factor)	Bladder: T0/Ta/Tis/T1/T2a/T2b/T3a/T3b/T4a/T4b/unknown

	n/other Urethra: T0/Ta/Tis/T1/T2/T3/T4/ unknown/other Renal pelvis: T0/Ta/Tis/T1/T2/T3/T4/ unknown/other Ureter: T0/Ta/Tis/T1/T2/T3/T4/unknown/other
Staging (TNM classification): Metastases to regional lymph nodes (N factor)	Bladder: N0/N1/N2/N3/unknown Urethra: N0/N1/N2/unknown Renal pelvis: N0/N1/N2/unknown Ureter: N0/N1/N2/unknown
Staging (TNM classification): Distant metastasis (M factor)	Bladder: M0/M1a/M1b/unknown/other Urethra: M0/M1/unknown/other Renal pelvis: M0/M1/unknown/other Ureter: M0/M1/unknown/other
Clinical Stage: Bladder	0a/0is/I/II/IIIA/IIIB/IVA/IVB
Clinical Stage: Urethra	0a/0is/I/II/III/IV
Clinical Stage: Renal pelvis	0a/0is/I/II/III/IV
Clinical Stage: Ureter	0a/0is/I/II/III/IV
Presence/absence of distant metastasis	presence/absence/unknown
Site of distant metastasis	lung/liver/adrenal/pancreas/kidney/spleen/bone/ distant lymph nodes/other
Presence or absence of visceral metastasis	presence/absence
Presence or absence of non-visceral metastasis	presence/absence
Number of metastatic organs	Single organ metastasis/multiple organ metastasis
Number of metastases in one organ	single/multiple
Number of distant metastases	single ("single organ metastasis" and "single")/multiple ("multiple organ metastasis" + "single organ metastasis" and "multiple")
Presence/absence of local recurrence	presence/absence/unknown
Presence or absence of past medical history	presence/absence/unknown
Details of past medical history	interstitial lung disease/chronic obstructive pulmonary disease (COPD)/auto-immune

	disease/cerebrovascular disorder/cardiovascular disorder/diabetes mellitus/other
Presence or absence of complication	presence/absence/unknown
Details of Complication	interstitial lung disease/chronic obstructive pulmonary disease (COPD)/auto-immune disease/cerebrovascular disorder/cardiovascular disorder/diabetes mellitus/other
Presence/absence of concomitant medication with steroid or immunosuppressant	presence/absence/unknown
Regimen for first-line chemotherapy	gemcitabine + cisplatin/gemcitabine + carboplatin/MVAC/dose dense-MVAC/other
Best overall response to first-line chemotherapies	CR/PR/SD/PD

8 Statistical Analysis of Secondary endpoints

8.1 Efficacy endpoints

8.1.1 Time to treatment failure (TTF) of avelumab

Target : Analysis set

population

n

Endpoint : Time to treatment failure (TTF) of avelumab

Statistical analysis : For the endpoint, the median and its 95% confidence interval will be calculated using the Kaplan–Meier method. In addition, the Kaplan–

Meier curve will be plotted, and the TTF rate for every 2 months and its 95% confidence interval will be calculated. Greenwood's formula will be used to calculate the confidence interval for the TTF rate.

In order to evaluate the overall observation period of the study, the median observation period will be calculated by estimating the reverse KM curve in which censoring patients are regarded as patients with events and patients with events are regarded as censoring patients.

In addition, as a sensitivity analysis, " interruption due to being well-controlled" will be treated as an event based on the day when death or discontinuation was observed before the date of the last

observation, and if no death or discontinuation or death occurred before the date of the last observation, data will be censored at the date of the last observation.

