9.2.2. Secondary endpoints

Efficacy endpoint

- Time to treatment failure (TTF) of avelumab

Definition of TTF is provided in 20. The following avelumab treatment data will be collected:

- 1) Date of start and end of avelumab administration
- 2) Dosage of avelumab
- 3) Date of avelumab discontinuation and interruption
- 4) Reason for avelumab discontinuation and interruption
- 5) Date of last survival confirmation

- Real-world progression-free survival (rwPFS)

Definition of rwPFS is provided in 20. The following data will be collected:

- 1) Date of start of avelumab treatment (administration)
- 2) Date of first disease progression or death due to any cause, whichever came first
- 3) Date of last survival confirmation

- Objective Response Rate (ORR)

ORR is defined in 21. The following data will be collected:

- 1) Tumor assessment (CR, PR, SD, PD)

- rwPFS from chemotherapy (rwPFS-c)

Definition of rwPFS-c is provided in Section 9.2.3.4. The following data will be collected:

- 1) Date of start of 1L Cht (administration)

- 2) Date of first disease progression or death due to any cause during avelumab treatment, whichever came first
- 3) Date of last survival confirmation

Safety endpoints

- Corticosteroid therapy for immune-related adverse events (irAEs)
The following data will be collected:
 - 1) Date of treatment
 - 2) Drug name of corticosteroid
 - 3) Starting dose of corticosteroid
 - 4) Duration of corticosteroid treatment
- Premedication for potential infusion-related reaction of avelumab
The following data will be collected:
 - 1) Presence of premedication for infusion-related reaction of avelumab
 - 2) Drug name used for premedication for infusion-related reactions of avelumab
- Treatment for infusion-related reaction of avelumab
The following data will be collected:
 - 1) Presence of treatment for infusion-related reaction of avelumab
 - 2) Drug name used for treatment for infusion-related reaction of avelumab
- Regimen after avelumab maintenance therapy
The following data will be collected:
 - 1) Medication for UC after avelumab maintenance therapy (drug name, start date of treatment, end date of treatment)
- Hematological test (after the start of 1L Cht)
The following data will be collected:
 - 1) Red blood cell count/ hemoglobin/ hematocrit/ white blood cell count (neutrophils, eosinophils, basophils, monocytes, lymphocytes)/ platelet count/ C-reactive protein (CRP)/ total protein/ albumin/ AST/ ALT/ LDH/ BUN/ creatinine/ Na/ K/ Cl

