5.5 Derived variable

The items and definitions of variables whose derivation is necessary at the time of statistical analysis are shown below.

Continuous variable

Item	Derivation method
Treatment-free interval: Time from the end date of first-line chemotherapy to the start date of avelumab administration (days)	Start date of initial administration with avelumab – end date of first-line chemotherapy administration + 1
Duration of treatment of first-line chemotherapy (days)	End date of first-line chemotherapy administration – start date of first-line chemotherapy administration + 1
Duration of treatment (irAE treatment) of corticosteroid (days)	End date of corticosteroid administration – start date of corticosteroid administration + 1
Time to treatment failure of avelumab (TTF)	Defined as the period from the date of start of avelumab to the date of end of treatment* for any reasons including death. If there is no record of end of treatment, patients will be censored at the date of last observation during the study period. *The following sensitivity analysis will also be performed. Considering its clinical meaning, "interruption due to being well-controlled" does not correspond to "treatment failure"; it should be treated as an event on the day when the death or discontinuation was observed prior to the last observation date. If no death or discontinuation occurred before the date of the last observation, data will be censored at the date of the last observation.
Real-world progression-free survival (rwPFS)	Defined as the period from the start date of avelumab maintenance therapy to the date of first

	
disease progression (clinical evaluation based on imaging examinations, laboratory tests, and pathological tests, as well as other evaluations by the investigators of each institution) or death from any cause, whichever occurs earlier.
 
If there is no record of death or disease progression, patients on second or later lines (following avelumab maintenance therapy) will be censored at the start of the second-line treatment, and patients on only avelumab maintenance therapy will be censored at the date of the last visit during the study, based on the medical record.

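### In the TTF sensitivity analysis, starting second-line therapy during a 'well-controlled' pause is not an event, so time on the next therapy can be counted as avelumab TTF

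*SAP*

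**What the plan says.** The main TTF analysis (SAP 5.5) runs from the start of avelumab "to the date of end of treatment* for any reasons including death". An asterisk on that definition leads to the sensitivity analysis, where a pause because the disease is well controlled is not treatment failure.

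For a patient with such a pause, SAP 5.5 states that "it should be treated as an event on the day when the death or discontinuation was observed prior to the last observation date". It continues: "If no death or discontinuation occurred before the date of the last observation, data will be censored at the date of the last observation". SAP 8.1.1 repeats the rule with a slip in the wording: "if no death or discontinuation or death occurred before the date of the last observation, data will be censored".

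The data behind the rule are listed in Protocol 9.2.2. One treatment item is "Date of avelumab discontinuation and interruption", with the reason collected as a further item. Subsequent treatment is collected as "Medication for UC after avelumab maintenance therapy (drug name, start date of treatment, end date of treatment".

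**The concern.** The sensitivity analysis exists to give TTF its clinical meaning: a patient resting from avelumab because the disease is controlled has not failed treatment. That reasoning stops applying once the patient starts another UC therapy. From then on avelumab maintenance is over, whatever the reason for the pause.

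The rule works for a patient who resumes avelumab and later stops, because that stop is a discontinuation. It is open for a patient who never resumes. Avelumab is already off, so the move to second-line therapy is an event only if someone also enters a discontinuation. If nobody does, time on the next drug is credited to avelumab, either as failure-free follow-up to the last observation or as time up to death. The contrast between main and sensitivity TTF would then partly reflect second-line time and not only the pause.

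**Working it through.** The plan gives no figure to reproduce. The check is of the rule itself, then one worked patient, then an illustration of size.

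**1. The rules side by side**

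| Source | What ends the patient's time |
|---|---|
| Main TTF, SAP 5.5 | End of treatment for any reason, including death |
| Sensitivity TTF after a pause, SAP 5.5 and 8.1.1 | Death or discontinuation; otherwise censored at last observation |
| rwPFS, SAP 5.5 | Progression or death; without either, a patient on a later line "will be censored at the start of the second-line treatment" |

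The SAP therefore already uses the second-line start date for rwPFS, but not for the sensitivity TTF. Neither document defines discontinuation as distinct from interruption. No visible rule turns a pause into a discontinuation when a new regimen starts.

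**2. One hypothetical patient**, using the SAP 5.3 day count (target date − start date + 1). Avelumab starts 1 March 2021 and is paused as well controlled on 1 October 2021. Second-line therapy starts 1 February 2022. The patient is alive on 30 June 2022, with no separate discontinuation entry.

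- Main analysis, if the pause is taken as end of treatment (the asterisk implies this; it is not stated outright): event at day 214 + 1 = 215.
- Sensitivity rule as written: censored at day 486 + 1 = 487.
- Sensitivity rule with second-line start as an event: event at day 337 + 1 = 338.

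The rule as written credits 487 − 338 = 149 days on second-line therapy to avelumab TTF. At 30 days per month (SAP 5.3), this patient counts as failure-free at months 12, 14 and 16 (days 360, 420 and 480). Had the patient died after day 338, the event would fall at death instead.

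**3. Illustration of size.** This is a Kaplan–Meier simulation of 200,000 patients. Only the follow-up range comes from the documents: index dates 24 February to 30 November 2021 with close on 30 June 2022, that is 212 to 491 days, simulated as uniform over 7 to 16.1 months. The rest is assumed:

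- time to end of treatment is exponential with median 4 or 6 months;
- 2% to 20% of treatment ends are well-controlled pauses;
- the median time from pause to the start of second-line therapy is 6 months.

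Deaths after the pause are left out, so the as-written columns are a worst case. The 12-month TTF rates are:

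| Main median | Share of pauses | As written, none recorded | As written, half recorded | Second-line start is an event | Worst-case gap (points) |
|---|---|---|---|---|---|
| 6 months | 2% | 26.5% | 26.1% | 25.7% | 0.8 |
| 6 months | 5% | 28.9% | 27.9% | 26.8% | 2.1 |
| 6 months | 10% | 32.5% | 30.5% | 28.5% | 4.0 |
| 6 months | 20% | 40.0% | 36.0% | 31.9% | 8.1 |
| 4 months | 2% | 14.3% | 13.8% | 13.2% | 1.1 |
| 4 months | 5% | 17.0% | 15.7% | 14.4% | 2.6 |
| 4 months | 10% | 21.3% | 18.8% | 16.4% | 4.9 |
| 4 months | 20% | 30.1% | 25.1% | 20.0% | 10.1 |

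Recorded means that a discontinuation is entered at the switch. If every affected patient has one, the gap is zero. The median moves less at low pause rates: with a 6-month main median, the worst case is 6.18 against 6.12 months at 2%, and 7.05 against 6.66 months at 10%.

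**The case against.** The strongest reply is that sites will probably record a discontinuation. Data collection was planned to start on 1 July 2022, the day after observation closed, so the person abstracting the chart sees the whole course. Dates and reasons are requested for both interruption and discontinuation, and Protocol 9.7 provides for data queries. The documents also describe second-line therapy as coming after avelumab maintenance, so a natural reading is that a patient on second line has discontinued. This stands to the extent that the effect may be small or nil. It does not close the gap: the link is never stated for TTF, and the data-entry instructions are not among the documents.

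A second reply concerns consequence, and it stands in full. The primary endpoint is baseline characteristics, no decision rests on this curve, and the main TTF, rwPFS, rwPFS-c and response analyses are untouched.

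A reader might go further and infer that leaving out progression is an error too, since a paused patient's TTF can exceed the same patient's rwPFS. The documents do not support that. TTF is time to end of treatment (Protocol 9.2.3.1, SAP 5.5), and progression is not a TTF event for any patient. Someone who progresses but stays on avelumab has no TTF event until treatment ends, so TTF can exceed rwPFS in the main analysis as well. Adding progression for paused patients alone would put two event definitions on one curve. Second-line start differs, because it marks the end of avelumab maintenance in the documents' own terms.

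**Conclusion.** The gap is real but narrow. As written, a paused patient on second-line therapy can count as not having failed avelumab, provided that no later discontinuation is recorded. For any affected patient the rule gives a TTF that is too long and never one that is too short.

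The documents do not show that this happens, or how often. The patient number is redacted, and the share of well-controlled pauses and the recording practice are not given. The simulated gaps of 0.8 to 10.1 points at 12 months rest on assumed inputs and worst-case recording; they show what the size depends on and are not an estimate for this study. Severity is low: the point is worth correcting because the correction is cheap and removes a one-directional error.

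**What to change.** In SAP 5.5 and 8.1.1, define the sensitivity event for a patient with a well-controlled interruption as the first of recorded discontinuation, start of subsequent UC therapy, or death. Censor at last observation only if none of these occurred. Correct the repeated word in 8.1.1 in the same edit, and report how many patients are reclassified. Do not add progression to the event list; if it is of interest, show it as an extra descriptive variant, labelled as such.

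The cost is one sentence in each section. No new data are needed, because the start date of subsequent therapy is already collected under Protocol 9.2.2. The derivation rule is also the practical place to settle this, since data collection was planned to end on 30 November 2022 and SAP version 1.1 is dated 21 December 2022. The downside is that the sensitivity curve may be slightly lower. If sites recorded the discontinuation at or before the switch, nothing changes.

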8.1.2 Real-world progression-free survival (rwPFS)

Target : Analysis set

population

n

Endpoint : **Real-world progression-free survival (rwPFS)**

Statistical analysis : For the endpoint, the median and its 95% confidence interval will be calculated using the Kaplan–Meier method. In addition, the Kaplan–Meier curve will be plotted, and the rwPFS rate for every 2 months and its 95% confidence interval will be calculated. Greenwood’s formula will be used to calculate the confidence interval for the rwPFS rate.

In order to evaluate the overall observation period of the study, the median observation period will be calculated by estimating the reverse KM curve in which censoring patients are regarded as patients with events and patients with events are regarded as censoring patients.

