3.3 Study design

This study is a multicenter, non-interventional, retrospective, medical chart review of

locally advanced or metastatic UC patients who were prescribed avelumab as 1L maintenance therapy between 24 February 2021 and 30 November 2021 in Japan. All decisions regarding clinical management and treatment of the participating patients were made by the investigator as part of standard care in a real-world clinical setting and were not contingent upon the patient's participation in the study. Data will be collected if available per study site.

- Index date: The date of first prescription for avelumab between 24 February 2021 (launch date of avelumab) and 30 November 2021
- Observation period: Patients will be followed from index date to 30 Jun 2022

CCI

4 Endpoints

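### SAP 8.1.2 and 8.1.4 count a patient who starts a next line as no longer observed, so the rwPFS-based median for the study's observation period runs short, and one label gets different values

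*SAP*

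**What the plan says.** SAP 3.3 defines one observation period for the whole cohort: "Observation period: Patients will be followed from index date to 30 Jun 2022". Protocol 6 and 9.1 say the same.

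SAP 8.1.1 (TTF), 8.1.2 (rwPFS) and 8.1.4 (rwPFS-c) each state the same aim, "In order to evaluate the overall observation period of the study, the median observation period will be calculated by estimating the reverse KM curve", and each applies it to that section's own endpoint by a curve "in which censoring patients are regarded as patients with events and patients with events are regarded as censoring patients".

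The censoring rules being reversed are in SAP 5.5 and differ:

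- TTF: "If there is no record of end of treatment, patients will be censored at the date of last observation during the study period".
- rwPFS and rwPFS-c, with no progression or death on record but a later line of therapy: the patient "will be censored at the start of the second-line treatment".
- rwPFS and rwPFS-c, with no later line: "patients on only avelumab maintenance therapy will be censored at the date of the last visit during the study".

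The clock for TTF and rwPFS starts at avelumab. The clock for rwPFS-c starts at first-line chemotherapy.

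Protocol 9.2.2 collects the drugs and dates of treatment given after avelumab, and also the "Date of last survival confirmation".

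**The concern.** A reverse Kaplan-Meier curve estimates length of follow-up only if each censoring time is the time at which observation really ended. Censoring at a next-line start is an analysis convention for progression. It does not mean that the patient left the study: later regimens and survival status are still being abstracted from the chart. Once the indicators are flipped, each such patient becomes an end-of-observation event, at a date that may be months before 30 June 2022.

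The same label is also attached to three curves with different censoring rules and, in 8.1.4, a different starting point. The three values need not agree, and in these sections the SAP does not say which one is the study's follow-up. Minimum follow-up is only about 7 months, so readers will look at this figure when they judge how mature the results are.

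**Working it through.** **1. The plan's own figure.** Protocol 6 assumes at least 7 months of follow-up. Counting days as in SAP 5.3 (target − start + 1, 30-day months), 30 November 2021 to 30 June 2022 is 213 days; 213/30 = 7.1 months, so the stated figure is reproduced. The longest possible follow-up, from 24 February 2021, is 492 days (16.4 months). The plan states no median.

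**2. Target value.** Assume uniform entry over the window (not in the documents) and every patient observed to 30 June 2022. The proportion still observed at day t is

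G(t) = (492 − t)/279 for 213 ≤ t ≤ 492, and 1 before day 213.

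G(t) = 0.5 gives t = (213 + 492)/2 = 352.5 days, or 11.75 months. Without the +1 it is 351.5 days.

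**3. What the reversed rwPFS curve converges to.** Assume the time to leaving rwPFS is exponential with median m days, and that a share q of those exits is a next-line start without recorded progression or death. In the reversed curve the next-line starts add a hazard of q·ln2/m to the true end of observation, so the curve tends to

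R(t) = G(t) × 2^(−q·t/m).

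The reported median solves R(t) = 0.5. Worked case, m = 180 and q = 10%: at t = 333.4, G = 158.6/279 = 0.5685 and 2^(−0.1 × 333.4/180) = 0.8795; the product is 0.500.

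| q | m = 120 | m = 180 | m = 270 | Shortfall against 352.5 days |
|---|---|---|---|---|
| 0% | 352.5 | 352.5 | 352.5 | 0 days |
| 5% | 338.2 | 343.0 | 346.2 | 6 to 14 days |
| 10% | 323.8 | 333.4 | 339.8 | 13 to 29 days |
| 20% | 295.7 | 314.3 | 327.0 | 26 to 57 days |

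A simulation of 400,000 patients per cell agreed with the formula to within 1 day. A second simulation timed next-line starts by a shorter TTF-like distribution plus one month. It gave 10.7 to 11.3 months at 10% and 9.65 to 10.9 months at 20%, against 11.75: the same pattern, with a largest shortfall of (11.75 − 9.65) × 30 = 63 days.

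**4. TTF (8.1.1).** TTF is censored only at last observation, so no next-line term arises and R(t) = G(t). With TTF medians of 3, 5 and 8 months, the simulated reversal gave 11.70 to 11.76 months against 11.75. It costs precision: at an assumed n = 100 and TTF median of 5 months, the standard deviation of the estimate is 0.92 months, against 0.46 when follow-up is measured directly. It overstates follow-up only if patients are lost early after stopping avelumab. With a TTF median of 150 days and 10% or 20% of patients lost 30 days after stopping, true median follow-up is about 341 or 328 days, while the TTF reversal stays at 352.

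**5. rwPFS-c (8.1.4).** It uses the same next-line censoring, and its clock starts before the index date. With an assumed 3 to 8 months from chemotherapy start to avelumab, the reversed median was 17.4 to 17.7 months at q = 0% and 14.4 to 16.1 months at q = 30%. Neither range measures the defined period, whose median here is 11.75 months.

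**The case against.** The strongest reply is that endpoint-specific reversal is informative about endpoint maturity. A patient censored at a next-line start adds nothing further to rwPFS, and a survival-based figure would hide that. Different values for endpoints with different censoring rules are then to be expected. This is fair, and it is why relabelling is an acceptable repair. It does not rescue the stated aim, which is the observation period of the study, a single quantity with fixed dates.

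Second, progression is defined broadly, by investigator assessment on any evidence, so few patients may switch without a progression record. This also stands: at 0% the rwPFS reversal is unbiased, and the documents do not give the share.

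Third, parts of the SAP are redacted. A reader might infer that no survival-based follow-up estimate is planned; the documents do not support that inference. Such an estimate would still leave the labels in 8.1.1, 8.1.2 and 8.1.4 as they are.

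A reader might also infer that all the reversals are biased in the same way, TTF included. That is not so. In the reversed TTF curve, patients who stop avelumab are censored; they are not counted as having ended follow-up. The early-loss scenario under which TTF runs long is an assumption. Protocol 10.2.2 provides for data collection after transfer to another facility, which would limit such loss.

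**Conclusion.** The concern holds for rwPFS, and the same censoring rule carries over to rwPFS-c. As written, 8.1.2 yields a median that is too short for the defined observation period by an amount that depends on how many patients start a next line with no progression or death on record: nil at 0%, about 1 to 2 weeks at 5%, 2 to 4 weeks at 10% and 4 to 8 weeks at 20%. These sizes rest on uniform entry, exponential rwPFS with a median of 120 to 270 days, and complete observation to 30 June 2022. The direction does not depend on the exponential form.

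The label is also inconsistent across 8.1.1, 8.1.2 and 8.1.4. The TTF version is consistent but less precise, unless follow-up ends earlier in patients who have stopped avelumab.

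Only a descriptive follow-up figure is affected. It would be a mistake to read this as an error in the TTF, rwPFS or rwPFS-c estimates or their confidence intervals.

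**What to change.** Report the observation period once, from the index date, by reverse Kaplan-Meier on survival. In patients not known to have died, observation ends at the last survival confirmation, capped at 30 June 2022. Deaths are censored at the date of death. Do not substitute 30 June 2022 for patients who were not confirmed alive then, because that would overstate follow-up.

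Before programming, confirm that the eCRF records the date of death after progression. Protocol 9.2.2 lists only the first of progression or death, together with the last survival confirmation.

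In SAP 8.1.1, 8.1.2 and 8.1.4, either delete the reverse Kaplan-Meier sentence or relabel the values as endpoint-specific follow-up. If the rwPFS version is kept, report the number of patients censored at a next-line start beside it.

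The cost is a few lines of SAP wording and one short program, plus the eCRF check. No efficacy estimate changes.
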